The literature on opioid dependence has consistently demonstrated elevated levels of cortisol (12, 25-38) and catecholamines (12, 39-43) during the acute withdrawal phase. Human and animal

models postulate that long-term use of opioids induces hypoadrenalism through impairment of the hypothalamic-pituitary-adrenal (HPA) axis. Opioid withdrawal leads to marked elevations of cortisol as a result of excess ACTH secretion (26, 32, 35). This HPA activation persists following normalization of the adrenergic system, which led some authors to conclude that cortisol is a more sensitive indicator of opioid withdrawal than catecholamines (30, 32). A small study by Higgins et al. on 5 non-dependent subjects assessed acute opioid withdrawal after a single dose of morphine and observed a dose-dependent increase in cortisol levels when subjects were subsequently injected with naloxone (28). Despite the clinical relevance, several limitations reduce the applicability of those results to our study population, mainly the selection of opioid-dependent subjects and rapid induction of withdrawal – through injection of naloxone or abrupt cessation of opioid with support medications such as alpha₂-agonists. Since our subjects are mostly opioid-naive prior to hospitalization and will be gradually weaned off their opioids, the magnitude of increase in cortisol levels will likely be lower.

As for catecholamines, serum epinephrine and norepinephrine appear to increase rapidly following opioid withdrawal in numerous animal and human studies (12, 39-43). However, in contrast with cortisol, catecholamine levels decrease shortly following acute withdrawal. In a study of subjects undergoing rapid opioid detoxification, catecholamine levels peaked two hours following naloxone administration (12). A gradual opioid weaning as often seen in clinical practice is unlikely to be recognized through measurement of serum catecholamines.

3. Research objectives

Research question

What are the signs and symptoms of opioid-associated iatrogenic withdrawal syndrome (OIWS) in the adult ICU population?

Primary objective

To identify specific signs and symptoms of OIWS in mechanically ventilated adult ICU patients receiving at least 72 hours of regular opioids at the Montreal General Hospital (MGH) and the Royal Victoria Hospital (RVH) from February to October 2018

Secondary objective

To determine if the presence of OIWS is associated with an increase in serum cortisol.

4. Methods

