5.1.2 Statistical inference

To gauge for presence of evaluation bias, inter-rater agreement will be determined using Cohen's kappa. This test measures the extent to which physicians concur when assessing for presence of OIWS using the DSM-5 criteria. A kappa of ≥ 0.61 is indicative of good inter-rater agreement (70).

For secondary outcomes, baseline, weaning and change in cortisol levels will be compared between patients positive and negative for OIWS. A Student's t-test or a Wilcoxon signed rank test will be used. The test will be determined based on distribution and sample size.

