5.2 Sample size

Based on our experience with the WAAICUP studies, 88 patients were eligible to participate in the study in an 8-month period, of which around 50 consented (22). We thus aim to recruit 50 patients based on the feasibility of these previous studies.

6. Advantages and limitations

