6.2 Limitations

The study is susceptible to several limitations, most of them due to study design. Due to lack of randomization, the study is subject to confounding. A notable covariate is the concomitant administration of benzodiazepines, which is difficult to control for since ICU patients frequently receive both opioids and benzodiazepines, and there is significant overlap in their respective withdrawal symptoms. However, administration of benzodiazepines will be noted during daily evaluations. The study is also susceptible to the "clinical trial effect" bias, since the attending physicians are not blinded to patient enrollment in the study and may modify their management consequently. To control for observer bias, pre-tested standardized data collection forms will be used, but it does not eliminate it completely, as evaluations will be performed by different investigators.

Since the sample size was determined on the basis of feasibility rather than statistical power, no statistically significant associations can be made. Statistical analyses will thus be predominantly descriptive in nature.

The exclusion of patients with severe or moderate traumatic brain injury requiring ICP monitoring and osmotherapy reduces external validity. These patients are important consumers of opioids and are therefore at risk of developing OIWS. However, their clinical condition would make the adequate assessment of OIWS impossible.

7. Relevance of study

To our knowledge, this is the first prospective study that aims to describe the clinical presentation of OIWS in the adult ICU setting with a standardized approach, fulfilling an identified research gap (71). As mentioned, OIWS is a clinical entity associated with negative outcomes that is poorly understood in critically ill adults because of diagnostic challenges. With a more accurate description of the clinical presentation, it would be possible to develop reliable screening tools to identify patients most at risk of OIWS and to sensitize the clinician to adopt appropriate measures in their management. An accurate description of the clinical presentation of OIWS is the first step in a series of research advances aimed at correctly recognizing and managing OIWS in adult ICU patients.

8. Ethical considerations and patient consent

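### The cortisol objective, its significance tests and the stated limitation do not fit together, and no interval is planned to show what a non-significant result leaves open

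*Combined protocol and SAP*

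**What the plan says.** - **Section 3, Secondary objective:** "To determine if the presence of OIWS is associated with an increase in serum cortisol".
- **Section 5.1.2:** "baseline, weaning and change in cortisol levels will be compared between patients positive and negative for OIWS". On method: "A Student's t-test or a Wilcoxon signed rank test will be used", and "The test will be determined based on distribution and sample size". No alpha, sidedness, multiplicity rule or confidence interval is given.
- **Section 5.1.1:** cortisol levels and changes are summarised descriptively, by mean and SD or by median and IQR. A between-group difference with an interval is not mentioned.
- **Section 5.2:** "We thus aim to recruit 50 patients based on the feasibility of these previous studies".
- **Section 6.2:** because the size rests on feasibility and not on power, "no statistically significant associations can be made". The next sentence says the analyses will therefore be mostly descriptive.
- **Introduction and section 6.1:** the cortisol work is described as exploring a potential biomarker.
- **Section 2, Biomarkers:** compared with the cited work in opioid-dependent subjects, "the magnitude of increase in cortisol levels will likely be lower".
- **Section 4.4.2:** cortisol is measured only in patients who are not receiving exogenous corticosteroids.

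**The concern.** The objective asks a yes-or-no question about association, and 5.1.2 supplies tests to answer it. Section 6.2 then rules out one of the two possible test outcomes in advance. The reason it gives does not support that. A sample size chosen without a power calculation can still give p<0.05. What is lost is control over the chance of missing a real difference, so the caution needed is about non-significant results, and the plan does not state it.

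At stake is what the secondary objective can conclude. The two cortisol samples are taken for the study and are not routine care (section 8). They account for $900 of the $1,300 budget, and section 6.1 presents the biomarker work as novel. If the result is reported only as a p-value above 0.05, the reader cannot tell whether the data exclude a large rise or barely constrain it.

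**Working it through.** **The plan's own figure.** The target of 50 matches the number who consented earlier: 50 of 88 eligible, 50/88 = 56.8%. There is no power calculation to reproduce.

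**Inputs from the documents.** N = 50 (5.2). The one prospective adult incidence cited is 16.7%, and the retrospective range is 19.7 to 100% (sections 1 and 2). The protocol adopts neither as a design assumption.

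**Assumptions.** Two-sided alpha 5%; equal SD in the two groups; W+ share 16.7% to 50%; share not sampled because of corticosteroids 0% to 50%. The SD of cortisol change is not given, so results are in SD units.

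**Group sizes.**
- 16.7% W+, all sampled: 50 × 0.167 = 8.35, so 8 v 42.
- 16.7% W+, 30% unsampled: 50 × 0.70 = 35 and 35 × 0.167 = 5.8, so 6 v 29.
- 16.7% W+, 50% unsampled: 25 × 0.167 = 4.2, so 4 v 21.
- 50% W+, all sampled: 25 v 25, the most favourable split of 50.

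**Half-width of the 95% confidence interval** for the difference in means, in SD units: t(0.975, n1+n2−2) × √(1/n1 + 1/n2).
- 8 v 42: 2.011 × √(0.1250 + 0.0238) = 2.011 × 0.386 = 0.78.
- 6 v 29: 2.035 × √(0.1667 + 0.0345) = 2.035 × 0.449 = 0.91.
- 4 v 21: 2.069 × √(0.2500 + 0.0476) = 2.069 × 0.546 = 1.13.
- 25 v 25: 2.011 × √(0.0400 + 0.0400) = 2.011 × 0.283 = 0.57.

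**Power**, from the noncentral t with noncentrality d × √(n1·n2/(n1+n2)):

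| W+ v W- | CI half-width (SD) | Detectable at 80% power (SD) | Power, 0.5 SD | Power, 0.8 SD | Power, 1.0 SD |
|---|---|---|---|---|---|
| 8 v 42 | 0.78 | 1.10 | 25% | 53% | 72% |
| 6 v 29 | 0.91 | 1.29 | 19% | 41% | 58% |
| 4 v 21 | 1.13 | 1.60 | 14% | 29% | 42% |
| 25 v 25 | 0.57 | 0.81 | 41% | 79% | 93% |

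**Reading the results.**
1. In the t-test, the half-width is also the smallest observed difference that reaches p<0.05. At 8 v 42, any observed difference above 0.78 SD is significant, so a significant association is possible and the statement in 6.2 does not follow.
2. An observed difference of exactly zero would still leave a rise of up to 0.78 SD (8 v 42) or 0.91 SD (6 v 29) inside the interval, and 0.57 SD even at 25 v 25. A positive but non-significant difference leaves more open.
3. The p-value shows neither of these facts; the interval shows both.

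**The case against.** The plan is candid. It says the size was not set by power, calls cortisol exploratory and describes its analyses as mostly descriptive, which leaves room for a few tests. Read in context, the sentence in 6.2 is a loosely worded caveat. If the descriptive summaries in 5.1.1 are reported by group, a reader could derive an interval, at least for the means. All of this stands, and it keeps the point small. It does not remove the mismatch: the objective still says determine, the tests are still planned, and nothing says how a non-significant result will be read.

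Three stronger readings are tempting, and the documents do not support them.
- **A null result is likely.** No effect size or SD is given. Section 2 expects only a smaller rise than one it describes as marked without quantifying it. Non-significance is more likely than not only for true differences below about 0.77 SD at 8 v 42; at 1.0 SD, power there is 72%. The 16.7% share may also be too low, because 5.1.1 makes a patient W+ on any single positive day and counts discordant ratings as positive.
- **A null result would answer the objective wrongly.** That needs both a real difference and a reader who takes non-significance as no association. Nowhere do the documents plan that interpretation.
- **Either p-value contradicts the plan.** A non-significant result contradicts nothing. Only a significant one conflicts, and only with 6.2 taken literally.

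**Conclusion.** The point holds as a minor one about consistency and reporting. Sections 3, 5.1.2 and 6.2 need to be reconciled, and the reasoning in 6.2 is incorrect: a feasibility-based sample leaves power uncontrolled and a non-significant result inconclusive, but does not rule out a significant one.

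The interval half-width is about 0.78 SD at 8 v 42, 0.91 SD at 6 v 29 and 0.57 SD at best. These figures rest on an assumed two-sided 5% level, equal SDs, and assumed W+ and unsampled shares. The exact width is uncertain, but in every scenario tried a non-significant p-value alone could leave a rise of more than half an SD open.

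**What to change.** 1. **Section 5.1.2:** make the W+ minus W- difference in cortisol change, with its 95% confidence interval, the main secondary result. Use a mean difference, or a rank-based shift for two independent groups if the data are skewed. The signed rank test now named is a paired method, whereas W+ and W- are separate patients. Tests of baseline, weaning and change can stay if labelled exploratory; dropping them is optional.
2. **Section 3:** word the secondary objective as exploring or estimating the association, in line with the introduction and section 6.1.
3. **Section 6.2:** replace the sentence with: the study was not powered for these comparisons, p-values are exploratory, and an interval that includes zero will not be read as absence of association.

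The cost is a few lines of wording and one interval from data already collected. The downside is that the interval will be visibly wide.

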Paper/Poster	Material	\$200.00
Total		\$1,300.00

[figure not shown]
11. Appendices

Appendix I. Research strategy in Medline

Search	Terms
A1: Opioids	exp Narcotics/ or Narcotics, Pharmacological Action/ or exp Opiate Alkaloids/ or exp Fentanyl/ or exp Meperidine/ or exp Morphine Derivatives/ or exp Methadone/ or narcoti*.mp. or opioid.mp. or opium.mp. or opiate.mp. or remifentanil.mp. or fentanyl.mp. or sufentanil.mp. or alfentanil.mp. or codeine.mp. or morphine.mp. or oxycodone.mp. or hydrocodone.mp. or hydromorphone.mp. or methadone.mp. or meperidine.mp.
A2: Sedatives or analgesics	"Hypnotics and Sedatives"/ OR "Hypnotics and Sedatives, Pharmacological Action"/ OR Narcotics, Pharmacological Action/ OR Conscious Sedation/ OR Deep Sedation/ OR exp Narcotics/ OR exp Opiate Alkaloids/ OR exp Fentanyl/ OR exp Meperidine/ OR exp Benzodiazepines/ OR exp Morphine Derivatives/ OR exp Methadone/ OR Clonazepam/ OR Bromazepam/ OR hypnotic.mp. OR sedative.mp. OR sedation.mp. OR narcoti*.mp. OR opioid.mp. OR opium.mp. OR opiate.mp. OR remifentanil.mp. OR fentanyl.mp. OR sufentanil.mp. OR alfentanil.mp. OR codeine.mp. OR morphine.mp. OR oxycodone.mp. OR hydrocodone.mp. OR hydromorphone.mp. OR methadone.mp. OR meperidine.mp. OR benzodiazepine.mp. OR diazepam.mp. OR lorazepam.mp. OR midazolam.mp. OR clonazepam.mp. OR alprazolam.mp. OR oxazepam.mp. OR temazepam.mp. OR bromazepam.mp. OR flurazepam.mp. OR chlordiazepoxide.mp. OR clobazam.mp. OR clorazepate.mp. OR nitrazepam.mp. OR triazolam.mp.
B: Iatrogenic withdrawal	Substance Withdrawal Syndrome/ OR Iatrogenic Disease/ OR Withholding treatment/ OR substance withdrawal.mp. OR drug withdrawal.mp. OR taper.mp. OR tapered.mp. OR tapering.mp. OR wean.mp. OR weaned.mp. OR weaning.mp. OR abstinence.mp. OR iatrogenic disease.mp. OR "withholding treatment".mp. OR "withholding treatment".mp.
C: ICU	exp Critical Care/ OR Subacute Care/ OR Postoperative Care/ OR exp Intensive Care Units/ OR Critical Illness/ OR intensive care.mp. OR critical care.mp. OR ICU.mp. OR PICU.mp. OR subacute.mp. OR postoperative.mp. OR post-operative.mp. OR burn unit.mp. OR burn centre.mp. OR burn center.mp. OR coronary care.mp. OR respiratory care.mp. OR critical illness.mp. OR critically ill.mp.
D: Tools	Decision Trees/ OR algorithms/ OR Checklist/ OR Questionnaires/ OR scale.mp. OR scaling.mp. OR score.mp. OR scoring.mp. OR tool.mp. OR checklist.mp. OR check-list.mp. OR questionnaire.mp. OR instrument.mp. OR WAT.mp. OR WAT-1.mp. OR withdrawal assessment tool.mp. OR decision tree.mp. OR algorithm.mp. OR sedation withdrawal score.mp. OR "opioid and benzodiazepine withdrawal score".mp. OR OBWS.mp. OR Sophia Observation Withdrawal.mp.
E1: Signs and symptoms	exp "Signs and Symptoms"/ OR exp Neurological Examination/ OR Symptom Assessment/ OR exp Vital Signs/ OR Facial Expression/ OR (symptom* OR anamne* OR dysphor* OR nause* OR vomit* OR muscle ach* OR lacrim* OR rhinorrhea OR pupil* dilat* OR piloerection OR sweat* OR diarrhea OR yawn* OR fever OR temperature OR insomnia OR shiver* OR sleep disturbance OR tremor OR anxiety OR agitat* OR suction* OR irritab* OR grimac* OR startl* OR muscle tone OR

	((uncoordinat* OR repetitive) AND movement) OR sneez* OR tachypnea OR mydriasis OR deliri* OR seiz* OR convuls*).mp.
E2: Biomarkers	exp Biomarkers/ OR "Biomarkers, Pharmacological"/ OR Monitoring, Physiologic/ OR Drug Monitoring/ OR Neuromuscular Monitoring/ OR Neurophysiological Monitoring/ OR (stress hormone OR cortisol OR cortisone OR catecholamines OR ((bio OR biological OR lab OR laboratory OR serum OR plasma OR endpoint? OR end-point?) ADJ (marker? OR surrogate?))).mp.
Run #1 (F)	A1 AND B AND C AND D AND E1
Run #2 (G)	(A1 AND B AND C AND D AND E2) NOT F
Run #3 (H)	(A2 AND B AND C AND D AND E1) NOT (F OR G)
Run #4 (I)	(A2 AND B AND C AND D AND E2) NOT (F OR G OR H)
Run #5 (J)	A1 AND B AND E2 (NOT F OR G OR H OR I)
Run #6 (K)	A2 AND B AND E2 (NOT F OR G OR H OR I OR J)

Appendix II. Study procedure

Appendix III. Dependent variables: signs and symptoms of OIWS (4, 15, 19, 20, 24)

Category	Signs and symptoms	Definition	Type of variable
Central nervous system symptoms	Agitation	During ICU hospitalization: Highest RASS score recorded in the previous 24h ^a according to nurse assessment ^{b, c}	Qualitative ordinal
		RASS -5 to 0, 1 (restlessness) or ≥ 2 (agitation)	Qualitative ordinal
		After ICU transfer to another ward: Agitated Behavior Scale (ABS) score during evaluation ≤ 21: No agitation; ≥ 22: agitation	Qualitative ordinal
	Anxiety	According to patient or nurse assessment in the previous 24h	Qualitative nominal (dichotomous)
	Dysphoria	According to physician DSM-5 evaluation	Qualitative nominal (dichotomous)
	Fever	Highest temperature value (°C) according to nurse assessment in the previous 24h	Quantitative continuous
		Temperature ≥ 38.3 degrees in the previous 24h	Qualitative nominal (dichotomous)
	Hallucinations	Patient seems to see, hear or feel things that are not there in the previous 24h, according to patient or nurse assessment	Qualitative nominal (dichotomous)
	Insomnia/sleep disturbance	Number of hours of sleep/night between 10PM and 6AM the night before evaluation according to nurse assessment	Quantitative discrete
		Lack of sleep defined as less than 4 hours of continuous sleep between 10PM and 6AM	Qualitative nominal (dichotomous)
	Startle to stimulus	Startle occurs when patient is stimulated verbally or by light touch during evaluation	Qualitative nominal (dichotomous)
	Time to regain calm post-stimulus	Time (minutes) needed to regain calm post-stimulus	Quantitative continuous
		Normal: < 2 min; Increased: 2 to 5 min; High: > 5 min	Qualitative ordinal
	Seizure	Presence not explained by metabolic disturbances or history of seizures in the previous 24h according to medical chart	Qualitative nominal (dichotomous)
Tremor	Presence of trembling, involuntary sustained rhythmic movements of hands and/or	Qualitative nominal (dichotomous)	

		feet during evaluation or according to nurse assessment in the previous 24h	
	Pupil size	Size (mm) according to nurse assessment in the previous 24h ≤ 2 mm, > 2 mm	Quantitative continuous Quantitative discrete (dichotomous)
	Yawning	Number of yawns in the previous 24h according to nurse assessment If ≥ 2 yawns observed during evaluation or in the previous 24h according to nurse assessment	Quantitative continuous Quantitative discrete (dichotomous)
Cardiac symptoms	Hypertension	Highest Systolic blood pressure (mmHg) according to nurse assessment in the previous 24h	Quantitative continuous
		Highest MAP (mmHg) according to nurse assessment in the previous 24h	Quantitative continuous
	Tachycardia	Highest HR in the previous 24h	Quantitative continuous
		Lowest heart rate in previous 24h	Quantitative continuous
		Is patient on a beta-blocker ; Yes or No	Qualitative nominal (dichotomous)
Respiratory symptoms	Frequent suction	Number of times patient required endotracheal suctioning in the previous 24h according to nurse assessment	Quantitative continuous
	Lacrimation	Presence during evaluation or according to nurse assessment in the previous 24h	Qualitative nominal
	Rhinorrhea	Presence during evaluation or according to nurse assessment in the previous 24h	Qualitative nominal (dichotomous)
	Sneezing	Number of sneeze observed during evaluation or according to nurse assessment in the previous 24h	Quantitative continuous
		If more than 1 sneeze observed during evaluation or according to nurse assessment in the previous 24h	Qualitative nominal (dichotomous)
	Significant dyspnea	Highest respiratory rate (RR) recorded in the previous 24h according to nurse assessment	Quantitative continuous
		Lowest respiratory rate (RR) recorded in the previous 24h	Quantitative continuous

		according to nurse assessment	
Gastrointestinal symptoms	Diarrhea	Presence of ≥ 3 BMs (loose/watery stools), in past 24 hours according to nurse assessment	Qualitative nominal (dichotomous)
		Number of BM in the previous 24h according to nurse assessment	Quantitative continuous
		Rectal tube required (yes or no)	Qualitative nominal (dichotomous)
	Feeding intolerance (gastric residuals)	Present if nurse discontinued or decreased enteral feeding during previous 24h due to gastric residuals of more than 500 mL according to nurse assessment	Qualitative nominal (dichotomous)
	Nausea	Presence during previous 24h according to patient, nurse assessment or use of antiemetic medications such as dimenhydrinate and ondansetron (indication to validate with nurse when necessary)	Qualitative nominal (dichotomous)
Vomiting	Presence or absence of vomiting episode(s) or retching or gagging in the previous 24h according to nurse assessment	Qualitative nominal (dichotomous)	
Dermatologic symptoms	Mottling	Presence of violaceous marbled discoloration of the skin during evaluation or according to nurse assessment in the previous 24h	Qualitative nominal (dichotomous)
	Piloerection	Presence during evaluation or according to nurse assessment in the previous 24h	Qualitative nominal (dichotomous)
	Sweating	Presence without apparent reason (not caused by room temperature) during evaluation or according to nurse assessment in the previous 24h	Qualitative nominal (dichotomous)
Musculoskeletal symptoms	Bone, joint or muscle aches	Presence during evaluation or according to nurse assessment in the previous 24h	Qualitative nominal (dichotomous)
	Muscle cramps	Presence during evaluation or according to nurse assessment in the previous 24h	Qualitative nominal (dichotomous)
	Muscle tone	Presence during evaluation or according to nurse assessment in the previous 24h	Qualitative nominal (dichotomous)

		(e.g. clenching wrists and toes, hunched shoulders, abnormal tense position of head, arm or legs)	
	Uncoordinated/ repetitive movement	Presence of involuntary movements of arm and/or legs, muscle twitches, during evaluation or according to nurse assessment in the previous 24h	Qualitative nominal (dichotomous)

^a Previous 24h designate the interval between midnight of the previous day and midnight of the day on which evaluation of the signs and symptoms occurs. A fixed time frame was chosen to standardize collection of signs and symptoms.

^b Nurse assessment comprises written (i.e. notes in medical chart or patient flow sheet) and/or verbal communication.

^c On the day of transfer, patients will be evaluated from midnight of the previous day until time of evaluation. Following transfer to ward, patients will be evaluated from midnight of the current day to time of evaluation.

Appendix IV. Diagnostic and Statistical Manual of Mental Diagnosis-V (DSM-5): “Opioid Withdrawal” criteria.

Diagnostic criteria:

A. Presence of either of the following;

1. Cessation of (or reduction in) opioid use that has been heavy and prolonged (i.e., several weeks or longer).
2. Administration of an opioid antagonist after a period of opioid use.

B. Three (or more) of the following developing within minutes to several days after

1. Dysphoric mood.
2. Nausea or vomiting.
3. Muscle aches.
4. Lacrimation or rhinorrhea.
5. Pupillary dilation, piloerection, or sweating.
6. Yawning.
7. Fever.
8. Insomnia.

C. The signs or symptoms in Criterion B cause clinically significant distress or impairment in social, occupational, or other important areas of functioning.

D. The signs or symptoms are not attributable to another medical condition and are not better explained by another mental disorder, including intoxication or withdrawal from another substance.

Reference: Association AP. Diagnostic and Statistical Manual of Mental Disorders: DSM-5. 5th ed. Washington, DC: American Psychiatric Publishing; 2013.

Appendix V. Acute Physiology and Chronic Health Evaluation II (APACHE II) developed by Knaus et al.

PHYSIOLOGIC VARIABLE	HIGH ABNORMAL RANGE					LOW ABNORMAL RANGE			
	+4	+3	+2	+1	0	+1	+2	+3	+4
TEMPERATURE — rectal (°C)	≥ 41*	39*–40.9*		38.5*–38.9*	36*–38.4*	34*–35.9*	32*–33.9*	30*–31.9*	≤ 29.9*
MEAN ARTERIAL PRESSURE — mm Hg	≥ 160	130–159	110–129		70–109		50–69		≤ 49
HEART RATE (ventricular response)	≥ 180	140–179	110–139		70–109		55–69	40–54	≤ 39
RESPIRATORY RATE — (non-ventilated or ventilated)	≥ 50	35–49		25–34	12–24	10–11	6–9		≤ 5
OXYGENATION: A-aDO ₂ or PaO ₂ (mm Hg)									
a. FIO ₂ ≥ 0.5 record A-aDO ₂	≥ 500	350–499	200–349		< 200				
b. FIO ₂ < 0.5 record only PaO ₂					PO ₂ > 70	PO ₂ 61–70	PO ₂ 55–60	PO ₂ < 55	
ARTERIAL pH	≥ 7.7	7.6–7.69		7.5–7.59	7.33–7.49		7.25–7.32	7.15–7.24	< 7.15
SERUM SODIUM (mMol/L)	≥ 180	160–179	155–159	150–154	130–149		120–129	111–119	≤ 110
SERUM POTASSIUM (mMol/L)	≥ 7	6.6–9		5.5–5.9	3.5–5.4	3–3.4	2.5–2.9		< 2.5
SERUM CREATININE (mg/100 ml) (Double point score for acute renal failure)	≥ 3.5	2–3.4	1.5–1.9		0.6–1.4		< 0.6		
HEMATOCRIT (%)	≥ 60		50–59.9	46–49.9	30–45.9		20–29.9		< 20
WHITE BLOOD COUNT (total/mm ³) (in 1,000s)	≥ 40		20–39.9	15–19.9	3–14.9		1–2.9		< 1
GLASGOW COMA SCORE (GCS): Score = 15 minus actual GCS									
A Total ACUTE PHYSIOLOGY SCORE (APS): Sum of the 12 individual variable points									
Serum HCO ₃ (venous-mMol/L) [Not preferred, use if no ABGs]	≥ 52	41–51.9		32–40.9	22–31.9		18–21.9	15–17.9	< 15

B AGE POINTS:
Assign points to age as follows:

AGE(yrs)	Points
≤ 44	0
45–54	2
55–64	3
65–74	5
≥ 75	6

C CHRONIC HEALTH POINTS

If the patient has a history of severe organ system insufficiency or is immuno-compromised assign points as follows:
a. for nonoperative or emergency postoperative patients — 5 points
or
b. for elective postoperative patients — 2 points

DEFINITIONS

Organ Insufficiency or immuno-compromised state must have been evident prior to this hospital admission and conform to the following criteria:
LIVER: Biopsy proven cirrhosis and documented portal hypertension; episodes of past upper GI bleeding attributed to portal hypertension; or prior episodes of hepatic failure/encephalopathy/coma.

CARDIOVASCULAR: New York Heart Association Class IV.

RESPIRATORY: Chronic restrictive, obstructive, or vascular disease resulting in severe exercise restriction, i.e., unable to climb stairs or perform household duties; or documented chronic hypoxia, hypercapnia, secondary polycythemia, severe pulmonary hypertension (>40mmHg), or respirator dependency.

RENAL: Receiving chronic dialysis.

IMMUNO-COMPROMISED: The patient has received therapy that suppresses resistance to infection, e.g., immuno-suppression, chemotherapy, radiation, long term or recent high dose steroids, or has a disease that is sufficiently advanced to suppress resistance to infection, e.g., leukemia, lymphoma, AIDS.

APACHE II SCORE

Sum of **A** + **B** + **C** :

A APS points _____

B Age points _____

C Chronic Health points _____

Total APACHE II _____

Reference: Knaus W, Draper E, Wagner D, Zimmerman J. APACHE II: a severity of disease classification system. Crit Care Med. 1985;13(10):818-29.

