Once the patient begins the targeted opioid weaning of $\geq 10\%$, investigators will perform evaluations daily between 10am and 2pm. These evaluations will consist of using pre-tested data collection sheets to record signs and symptoms of possible OIWS, opioid doses, administered medications, laboratory values and other clinical data such as the RASS, CPOT and CAM-ICU scores. Data collection will be based on subject observation and interview when possible, nurse assessments, medical charts and laboratory results. Serum cortisol levels will be measured on the first day of opioid weaning (± 2 hours from dose decrease) and on the day patient is transferred to the ward or 72 hours from start of weaning whichever occurs first.

Once a weaning episode is identified, the physician collaborator will be contacted to perform daily DSM-5 evaluations. DSM-5 evaluations will be placed in opaque envelopes and investigators will be blinded to the results throughout the study. Additionally, for each patient, at least one inter-rater DSM-5 evaluation between 2 physician collaborators will be performed in order to assess interrater reliability. The two evaluations will be done within 2 hours of each other to minimize time-related discrepancies.

If opioid weaning is unsuccessful and opioid dose is re-increased, the subject will continue to be observed, however daily evaluations will only resume at the next weaning episode. Daily follow-up ends on day of transfer to the ward. One additional data collection and DSM-5 evaluation will be performed on the same day within 24 to 96 hours following transfer. Follow up ends 14 days after initial opioid weaning if patient remains in the ICU or if patient dies.

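### The look-back for signs is 24 h on ordinary ICU days, 34-38 h on the transfer day and about 10-14 h on the ward, yet section 5.1.1 pools all visits

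*Combined protocol and SAP*

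**What the plan says.** The definitions are in the footnotes to Appendix III.

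- Footnote a: "Previous 24h designate the interval between midnight of the previous day and midnight of the day on which evaluation" occurs, with the reason "A fixed time frame was chosen to standardize collection of signs and symptoms".
- Footnote b: nurse assessment covers written entries, verbal reports, or both.
- Footnote c, transfer day: "On the day of transfer, patients will be evaluated from midnight of the previous day until time of evaluation".
- Footnote c, ward: "Following transfer to ward, patients will be evaluated from midnight of the current day to time of evaluation".

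Section 4.5 gives the timing: "investigators will perform evaluations daily between 10am and 2pm". Daily follow-up includes the day of transfer. After that, "One additional data collection and DSM-5 evaluation will be performed on the same day within 24 to 96 hours following transfer". For patients who stay in the ICU or die, "Follow up ends 14 days after initial opioid weaning if patient remains in the ICU or if patient dies".

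Section 5.1.1 treats each day with a DSM-5 result as an episode. It tallies signs per episode and reports proportions with total episodes as denominator, compared between patients with at least one positive day (W+) and patients with none (W-). It has no rule that separates or adjusts for visit type.

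**The concern.** The primary outcome is the set of signs tallied per episode. A longer look-back gives a sign more time to be recorded, and a shorter one gives it less. Under footnote c the transfer-day record covers more time than an ordinary ICU record, and the ward record covers less. Both visits have a DSM-5 evaluation, so both enter the pooled tally as full episodes. At stake is whether a recorded frequency describes the patient's state or partly the type of visit, which is what footnote a set out to prevent.

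**Working it through.** **Inputs.** Window endpoints come from Appendix III, footnotes a and c. The visit time of 10am to 2pm comes from section 4.5; it is stated for the daily evaluations and assumed for the ward visit. The markers for footnotes a and c appear in the agitation row. I read both as general, since a defines a term used throughout the table and c describes whole evaluations.

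**Step 1: window lengths.** Footnote a's own figure reproduces: midnight to midnight is 24 h.

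- Transfer day: 24 + 10 = 34 h to 24 + 14 = 38 h.
- Ward: 10 h to 14 h.
- Ratio of transfer day to ward at the same clock time: 38/14 = 2.7 to 34/10 = 3.4.

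**Step 2: signs affected in the stated summary.** Section 5.1.1 reports proportions, so what matters is a sign in yes/no or category form with no bedside alternative. In Appendix III these are mainly fever, seizure, feeding intolerance, vomiting and diarrhea, plus highest RASS on the transfer day only, because agitation on the ward is scored with the ABS at the evaluation. The yes/no row for diarrhea refers to the past 24 hours rather than the defined term; read literally, it conflicts with footnote c. Suction and bowel-movement counts, blood pressure, heart rate and respiratory rate are affected only where those continuous values are themselves summarised.

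**Step 3: size for one record (illustration, two assumed models).**

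Model A, constant-rate onset: P(h) = 1 - (1 - p)^(h/24), where p is the frequency in a 24 h window.

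Model B, for p = 0.30 with half of such cases already present when the window opens: P(h) = 0.15 + 0.85 × [1 - (1 - q)^(h/24)], with q = 0.15/0.85 = 0.176 so that P(24) = 0.30.

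| Window | A, p = 0.10 | A, p = 0.30 | A, p = 0.50 | B, p = 0.30 |
|---|---|---|---|---|
| 10 h | 0.043 | 0.138 | 0.251 | 0.216 |
| 14 h | 0.060 | 0.188 | 0.333 | 0.241 |
| 24 h | 0.100 | 0.300 | 0.500 | 0.300 |
| 34 h | 0.139 | 0.397 | 0.625 | 0.354 |
| 38 h | 0.154 | 0.431 | 0.666 | 0.375 |

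A 30% sign becomes 40-43% (transfer day) and 14-19% (ward) under A, or about 35-38% and 22-24% under B.

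**Step 4: net effect for one patient.** Take two ordinary ICU days, p = 0.30, and the same clock time at both later visits.

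- Both visits, A: (0.60 + 0.138 + 0.397)/4 = 0.284 to (0.60 + 0.188 + 0.431)/4 = 0.305, that is -1.6 to +0.5 points.
- Both visits, B: (0.60 + 0.2161 + 0.3544)/4 = 0.2926 to (0.60 + 0.2410 + 0.3750)/4 = 0.3040, that is -0.7 to +0.4 points.
- Transfer day only, A: (0.60 + 0.397)/3 = 0.332 to (0.60 + 0.431)/3 = 0.344.
- Ward only, A: (0.60 + 0.138)/3 = 0.246 to (0.60 + 0.188)/3 = 0.263.

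**Step 5: share of episodes.** With k ordinary ICU visits and both later visits, the share on a window other than 24 h is 2/(k + 2): 50% at k = 2, 29% at k = 5, 17% at k = 10. A patient still in the ICU at day 14 contributes neither visit.

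**The case against.** Footnote c is an open exception, placed beside the rule and the same for every patient. It also has a purpose. Ordinary windows close at midnight, so running the transfer-day window on to the visit captures the last ICU hours, which no later ICU record would hold. The long and short windows nearly cancel when both visits occur, grouping is by patient, and section 6.2 calls the analysis predominantly descriptive, with 50 patients chosen on feasibility. All of this stands, and it limits the size. It does not make the records comparable, and nothing in the plan secures the cancellation.

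Three stronger readings are tempting but not supported.

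- A reader might infer that these signs come from charts alone. Footnote b also allows verbal nurse reports, and of the signs listed in step 2 only seizure is defined by the medical chart.
- A reader might infer that shifts in counts and maxima distort the primary summary. That summary is a proportion per episode; blood pressure, heart rate, respiratory rate and suction have no yes/no or category form in Appendix III.
- A reader might take footnote a's interval as the evaluation day itself, which would make both later windows short and remove the offset. Footnote c's two windows would then coincide, and its distinction would have no meaning.

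**Conclusion.** The point holds as a minor one. Following the plan exactly gives three look-back lengths, which section 5.1.1 pools without separation, so nurse- or chart-recorded signs are not comparable across visit types. For a single record the illustrated shift for a 30% sign is about +5 to +13 points on the transfer day and -6 to -16 points on the ward, across both onset models. Over four episodes with both visits it is at most -1.6 to +0.5 points. These sizes rest on assumed onset patterns and on the ward visit keeping the 10am-2pm slot.

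A reader might infer a bias between W+ and W-. The documents do not show one. It would need a different mix of visit types in the two groups, or a tally of only some of a patient's days. Section 4.4.1 notes that withdrawal has been associated with longer ICU stays, so the mix could differ, but the direction cannot be determined. The offset fails when only one of the two visits occurs (33-34% or 25-26% instead of 30% in step 4). It may also fail if only some days are tallied, and section 5.1.1 does not clearly say whether the negative days of W+ patients count.

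**What to change.** In footnotes a and c, define one 24 h window for every ICU, transfer-day and ward visit, and apply it to written and verbal nurse reports alike. Two versions would work.

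- **The 24 h ending at 10am on the evaluation day.** Consecutive daily windows tile without gaps. At the ward visit the window can reach up to 4 h before transfer, but only if the visit falls close to 24 h after it.
- **The 24 h ending at the evaluation.** Since the ward visit is 24-96 h after transfer, this window lies within the ward stay. Because daily visits range from 10am to 2pm, consecutive windows can leave gaps or overlaps of up to 4 h.

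Bring the diarrhea row into line with the defined term. If data are already collected under the present windows, report transfer-day and ward visits separately for the window-dependent signs, or show the tally with and without them. The cost is footnote and data-sheet wording and slightly more abstraction work.
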